# 4. LIST OF ABBREVIATIONS

Abbreviation	Definition
AE	adverse event
AESI	adverse event of special interest
ALT	alanine transaminase
aPTT	activated partial thromboplastin time
AST	aspartate transaminase
AUC	area under the concentration-time curve
AUC 0-24	area under the concentration-time curve from time 0 to 24 hours
AVF	arteriovenous fistula
BGP	bone Gla protein
BUN	blood urea nitrogen
β-hCG	beta-human chorionic gonadotropin
CBC	complete blood count
CFR	Code of Federal Regulations
CHD	coronary heart disease
CI	confidence interval
CKD	chronic kidney disease
cMGP	carboxylated Matrix Gla Protein
CMP	complete metabolic panel
C max	maximum plasma concentration
CPP	calciprotein particles
CRA	clinical research associate
CRO	contract research organization
CUA	Calcific Uremic Arteriolopathy (calciphylaxis)
CVA	cerebrovascular accident
dba	doing business as
DNA	deoxyribonucleic acid
dp-cMGP	desphospho-carboxylated Matrix Gla Protein
dp-ucMGP	dephosphorylated and uncarboxylated Matrix Gla Protein
eCRF	electronic Case Report Form
ECG	Electrocardiogram
EDC	electronic data capture
EFSA	European Food Safety Authority
EOS	End-of-Study (visit)
EOT	End-of-Treatment (visit)
ESRD	end-stage renal disease
FAO	Food and Agriculture Organization (of the United Nations)
FDA	Food and Drug Administration
FSI	first subject in
GCP	Good Clinical Practice

Abbreviation	Definition
GGCX	gamma glutamate carboxylase
Gla	gamma-carboxyglutamic acid
GLP	Good Laboratory Practice
HBeAg	hepatitis B "e" antigen
HBV	hepatitis B virus
HCV	hepatitis C virus
HDL	high-density lipoprotein
HIPAA	Health Insurance Portability and Accountability Act
HIV	human immunodeficiency virus
HPLC	high performance liquid chromatography
hs-CRP	high-sensitivity C-Reactive Protein
ICF	informed consent form
ICH	International Conference on Harmonisation
ID	Identification
IEC	Independent Ethics Committee
IND	Investigational New Drug application
INR	International Normalized Ratio
IOM	Institute of Medicine
IP	investigational product
IV	intravenous(ly)
KH2	vitamin K hydroquinone
Kt/V	measure of dialysis adequacy; K=dialyzer urea clearance, t=duration of the dialysis session, V=volume of urea distribution
LC/MS/MS	liquid chromatography tandem mass spectrometry
LDL	low-density lipoprotein
LSLV	last subject last visit
MedDRA	Medical Dictionary for Regulatory Activities
MGP	Matrix Gla Protein
MK-4	menaquinone-4
MK-7	menaquinone-7
mRNA	messenger ribonucleic acid
NADP	nicotinamide adenine dinucleotide phosphate
NOAC	novel oral anticoagulants
NOAEL	no-observed-adverse-effect-level
LSLV	last subject last visit
PCR	polymerase chain reaction
PIVKA-II	Protein Induced in Vitamin K Absence/Antagonist-II (also known as descarboxyprothrombin or des-gamma-carboxy prothrombin [DCP])
PK	Pharmacokinetic(s)
PT	preferred term
PTT	partial thromboplastin time

Abbreviation	Definition
RBC	red blood cell
RNA	ribonucleic acid
ROS	reactive oxygen species
RR	relative risk
SAE	serious adverse event
SD	standard deviation
SMF	Site Master File
SOC	System Organ Class
SRC	Safety Review Committee
TG	triglycerides
T-50	Time to Formation of Secondary Calciprotein Particles
TIA	transient ischemic attack
T max	time to maximum plasma concentration
ULN	upper limit of normal
USA/US	United States of America
USP	United States Pharmacopeia
VKD	vitamin K-dependent
VKOR	vitamin K oxidoreductase
VKORC1	vitamin K epoxide reductase C1
VKORC1L1	vitamin K epoxide reductase C1-Like-1
VKR	vitamin K reductase
WBC	white blood cell
WHO	World Health Organization

# 5. PROTOCOL SYNOPSIS

Study Title	A Phase 1, Prospective Safety Trial of EPN-701 in Subjects with Stable End Stage Renal Disease (ESRD) Receiving Outpatient Hemodialysis
Study Number	EPN-701-001
Clinical Development Phase	Phase 1
Indication	End Stage Renal Disease (ESRD) on hemodialysis
Study Design	This is a Phase 1, prospective, open label study to evaluate the safety, tolerability, and pharmacokinetics (PK) of EPN-701, administered once daily for 14 days in subjects with ESRD on a stable hemodialysis regimen.
Study Objectives	Primary Objectives:  To determine the safety and tolerability of EPN-701 (administered for two weeks at a daily dose of 10 mg) in subjects with ESRD on stable hemodialysis.
	
 
Secondary Objectives
 
To determine, in subjects with ESRD on stable hemodialysis, the plasma levels of the following biomarkers after two weeks of EPN-701 treatment relative to baseline: uncarboxylated MGP; uncarboxylated osteocalcin; Activated Protein C; and Protein Induced Vitamin K Absence-II (PIVKA-II).
 

	
 
Exploratory Objectives:
 
To determine the pharmacokinetic profile of EPN-701 in subjects with ESRD on stable hemodialysis.
 

	
 
To determine, in subjects with ESRD on stable hemodialysis, the plasma levels of the following biomarkers after two weeks of EPN-701 treatment relative to baseline: osteoprotegerin, Fetuin A, high-sensitivity C-Reactive Protein (hs-CRP) and Time to Formation of Secondary Calciprotein Particles (T-50 Test), including CPP size.
 

Study Population	A total of 15 eligible subjects with ESRD on a stable maintenance dialysis regimen will be enrolled and treated with EPN-701.
Inclusion Criteria	Subjects must meet all inclusion criteria to be enrolled in the study:  1. Male or female ≥18 years of age

- 2. Diagnosed with ESRD and treated with stable maintenance hemodialysis at least three times a week for at least three months prior to the first dose of study drug. Subjects may have missed (less than or equal to) 4 hemodialysis sessions within three months prior to enrollment, provided that the Principal Investigator deems them suitable for study participation.
- 3. Clinically stable medical condition, consistent with ESRD, as judged by the investigator based on the results of screening safety evaluations (physical examination, medical history, clinical laboratory tests, vital signs, and 12-lead electrocardiogram [ECG])
- 4. Written informed consent
- 5. Able and willing to comply with the requirements of the study protocol
- 6. For females of child-bearing potential:
  - Negative serum pregnancy test;
  - Abstinence (refraining from heterosexual intercourse) or use of an acceptable contraception for at least 1 month prior to screening, and willingness to continue for at least 1 month after the last study drug administration.

A woman is considered to be of childbearing potential if she is post-menarche, has not reached a postmenopausal state (≥ 12 continuous months of amenorrhea with no identified cause other than menopause), and has not undergone surgical sterilization (removal of ovaries and/or uterus, or bilateral tubal ligation).

Examples of acceptable contraceptive methods include: hormonal contraceptives that inhibit ovulation, hormone-releasing intrauterine devices, and copper intrauterine devices.

#### **Exclusion Criteria**

Subjects meeting any of the following exclusion criteria will be excluded from the study:

- 1. Chronic kidney disease not requiring hemodialysis
- 2. Acute kidney injury treated with hemodialysis
- 3. Diagnosis of confirmed calciphylaxis
- 4. History of any solid organ transplant
- 5. History of malignancy within 2 years of study enrollment, except for adequately treated carcinoma *in situ* of the cervix and non-melanoma skin carcinoma
- 6. History of any major surgery (defined as a surgical procedure involving the cranium, chest, abdomen, or pelvic cavity, or other procedure performed under general anesthesia) within 1 month prior to the first dose of study drug. Subjects with a recent (within <1 month) revision and/or placement of arteriovenous fistula (AVF) will be allowed to participate.

- 7. History of a major cardiovascular event (such as cerebrovascular accident [CVA], transient ischemic attack [TIA], myocardial infarction, unstable angina) within 1 month prior to the first dose of study drug.
- Any co-existing disease or condition that may compromise the safety of study participants and/or the integrity of the study, including, but not limited to:
  - Class C or Class D Cirrhosis of the liver
  - Known intestinal malabsorption
  - Inability to take oral medication
- 9. Life-expectancy <3 months
- 10. Known history or positive serology for Human Immunodeficiency Virus (HIV), positive serologies of E antigen or with polymerase chain reaction (PCR) positive titers for hepatitis B virus (HBV). Subjects with positive serologies for hepatitis C but with negative PCR for active virus will be allowed.
- 11. Severe infection requiring intravenous (IV) antibiotics within two weeks prior to the first dose of study drug.
- 12. Warfarin taken within two weeks prior to the first dose of study drug. Subcutaneous heparin, enoxaparin and novel oral anticoagulants (NOAC; such as apixaban) are permitted.
- 13. Treatment with an investigational drug within four weeks prior to the first dose of study drug.

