# Study Assessments & Schedule

A total of 15 consenting subjects meeting the study eligibility criteria will be enrolled and treated with EPN-701 10 mg (one 10 mg capsule to be taken orally once a day, at the same time each morning), for 14 days.

The expected duration of study participation for an individual subject is approximately five weeks, including up to one week for screening, two weeks of study treatment, and two weeks of post-treatment safety follow-up. Subjects will undergo a total of 14 visits during their study participation: Screening visit (within seven days prior to the first dose of study drug), three visits per week during the two-week treatment, and two-week safety follow-up periods (coinciding with the subject's hemodialysis schedule), and the End-of-Study (EOS)/Early Termination visit. Baseline assessments will be completed prior to the first study drug intake on Day 1. End-of-Treatment (EOT) assessments will be completed after the last dose of study drug on study Day 15 (or earlier in case of an early discontinuation of the study treatment). The EOS/Early Termination visit will occur two weeks after the last dose of study drug (on study Day 29).

Subjects will be monitored for adverse events (AEs), and concomitant medications will be recorded throughout their study participation (from screening through the EOS/Early Termination Visit). Additional safety assessments will include: physical examinations, safety laboratory tests (hematology, including complete blood count [CBC]; complete metabolic panel [CMP, including electrolytes, renal and liver function tests, and lipid profile]; and coagulation panel), vital signs measurements, and 12-lead ECG. In addition, occurrence of dialyzer clotting will be assessed at each dialysis session, and Kt/V (a measure of dialysis adequacy) will be calculated at baseline (as the average of the last three pre-study Kt/V values obtained as part of the subject's standard of care) and at the end of treatment.

Blood for PK assessments will be sampled as follows:

 On Day 1 (baseline) and Day 8 (Week 2, on-treatment): predialysis (at the time of needle placement, denoted as 0 hours), immediately followed by study drug administration, and then at 1 hour (+/- 5 minutes), 2 hours (+/- 5 minutes), 3 hours (+/- 5

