- [6] Standard 12-lead ECG recordings will be obtained within 60 minutes pre-dialysis at screening/baseline, at EOT (Day 15), and at EOS (Day 29). ECG recordings should be performed after the subject has been resting in a supine position for at least 5 minutes, and prior to other procedures scheduled at that same time (e.g., blood draws).

[7] Vital signs (including blood pressure, heart rate, respiratory rate, and oral body temperature) will be measured at screening, and (as part of their standard care on dialysis days) within 30 minutes pre-dialysis and within 30 minutes post-dialysis at each treatment visit (Visits 1 through 6), at EOT (Day 15), and EOS (Day 29).

- [8] All blood sampling will occur pre-dialysis (at the time of needle placement). Hematology panel includes: RBC count, hemoglobin, hematocrit, and WBC count with differential (neutrophils, eosinophils, lymphocytes, monocytes, basophils, and other cells), if clinically indicated. CMP includes: glucose, albumin, total protein, electrolytes (sodium, potassium, bicarbonate, chloride, calcium, magnesium, phosphate), renal function tests (BUN, creatinine), liver function tests (ALT, AST, bilirubin), and lipid profile (total cholesterol, LDL cholesterol, HDL cholesterol, and triglycerides). Coagulation panel includes: PTT, INR, and platelet count.
- [9] Serology for: HIV, HBV (hepatitis B "e" antigen [HBeAg] and PCR for the active virus [HBV DNA]); and HCV (HCV antibody and PCR for active virus [HCV RNA])
- [10] Women of child bearing potential must undergo a serum β-hCG pregnancy test within 7 days prior to the first dose of study drug, and the result must be negative for enrollment.
- [11] All medications (including over-the-counter medications) or therapy administered to the subject during the 30 days prior to the first dose of study drug will be recorded at screening/baseline. Any changes to concomitant medications will be documented regularly throughout the study.

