### 6.1 BACKGROUND ON VITAMIN K2

### 6.1.1 Vitamin K Metabolism and the Impact of Hemodialysis

Vitamin K is an essential enzymatic co-factor that is required for posttranslational modifications of vitamin K-dependent (VKD) proteins. Of the numerous VKD proteins, several are clinically relevant to ESRD patients. They include the central coagulation factors such as factors II, VII, IX, and X, as well as intercellular matrix proteins including matrix gamma-carboxyglutamic acid (Gla) protein (MGP) and osteocalcin (also referred to as bone Gla protein [BGP]). It has been proposed that vitamin K is reduced to vitamin K hydroquinone (KH2) via two pathways: a warfarin-sensitive pathway (by vitamin K epoxide reductase [VKORC1]) and a warfarin-resistant pathway (Tie and Stafford, 2016). It is only the reduced form of vitamin K that can function as a co-factor for gamma glutamate carboxylase (GGCX) which catalyzes the carboxylation of VKD proteins (Gallieni and Fusaro, 2014). Warfarin blocks the generation of vitamin K hydroquinone by acting as an inhibitor of the vitamin K recycling (Figure 1). The enzymatic carboxylation of glutamate residues results in further oxidation of vitamin KH2 to 2,3-epoxide Vitamin K. The final step of the vitamin K cycle requires the enzymatic reduction of vitamin K 2,3-epoxide back to its native structure. This step is catalyzed by VKORC1 and is a component of the vitamin K cycle along with warfarin (Figure 1) (Gallieni and Fusaro, 2014).

Figure 1 - Vitamin K Cycle

Conversion of glutamate (Glu) to g-carboxyglutamate (Gla) residues by g-glutamyl carboxylase (GGCX) (1) is essential for the activation of vitamin K-dependent (VKD) proteins. g-Carboxylation transforms undercarboxylated (ucVKD) into carboxylated (cVKD) proteins. Vitamin K hydroquinone (KH2) is oxidized to vitamin K epoxide (KO). KO is converted to vitamin K quinone by vitamin K epoxide reductase (2). A similar reductase enzymatic reaction (2) converts vitamin K quinone back into KH2. Another reductase, NAD(P)H-dependent vitamin K reductase (3), or DT-diaphorase, can also catalyze the same conversion into KH2. Warfarin inhibits the reductase activity (2) that is dithiol dependent but not the NADPH-dependent reductase (3), whose substrate can be dietary vitamin K.

Source: Gallieni and Fusaro. 2014

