# 9.6.3 Baseline and Concomitant Medications

All medications (including over-the-counter medications) or therapy administered to the subject during the 30 days prior to the first dose of study drug will be recorded at screening/baseline (including start date, medication name, dosage, frequency, and route of administration). Any contraindicated medications will be stopped or replaced by different medication and the subject will be required to observe the protocol-specified wash-out period (refer to Section 9.4.1 for details).

Any changes to concomitant medications will be documented regularly throughout the study.

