### 11.8 BIOMARKER ANALYSES

Pre-defined biomarker endpoints include:

- Plasma levels of the following biomarkers on Day 15 (end-of-treatment) and Day 22 compared to baseline:
  - Uncarboxylated MGP
  - Uncarboxylated osteocalcin
  - Activated Protein C
  - o PIVKA-II protein.

Exploratory biomarker endpoints include:

 Plasma levels of the following biomarkers on Day 15 (end-of-treatment) and Day 22 compared to baseline: osteoprotegerin, Fetuin A, hs-CRP, and Time to Formation of Secondary Calciprotein Particles (T-50 Test), including CPP size.

Biomarkers will be summarized in a similar manner as described for safety laboratory parameters, with a descriptive summary provided for each assessment time-point along with changes from baseline. Depending of the distribution of the biomarkers, transformations to minimize skew and outliers may be performed.

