#### 13.2 INFORMED CONSENT

The study will be conducted in accordance with FDA Code of Federal Regulations (CFR) Title 21, Part 50, Subpart B-Informed Consent of Human Subjects and the applicable local IRB requirements.

The investigator must obtain written informed consent from each prospective subject or they legally authorized representative after adequate explanation of the aims, methods, anticipated benefits, and potential hazards of the study, and before any study-related procedures, assessments, treatments, or protocol-required changes in the subject's ongoing management can be made. The clinical records for each subject should document the informed consent process and that written informed consent was obtained prior to participation in the study.

The consent forms will be revised each time there are changes to study procedures or when new information becomes available that may affect the willingness of the subject to participate. The final revised IRB-approved consent form(s) must be provided to the Sponsor for health authority submission purposes.

Subjects participating in the study must be re-consented to the most current version of the consent form, according to the applicable local law and IRB policy. A copy of each signed consent form must be provided to the subject or the subject's legally authorized representative. All signed and dated consent forms must remain in each subject's study file or in the site file and must be available for verification by study monitors at any time.

Subject authorization to allow use and disclosure of personal health information in compliance with the U.S. Health Insurance Portability and Accountability Act (HIPAA) of 1996 may be included in the consent form or a separate HIPAA Authorization Form may be utilized, as per the site policies.

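### Subjects who stopped warfarin just over two weeks before Day 1 may still be recovering, and the biomarker analysis has no summary that would show it

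*Combined protocol and SAP*

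**What the plan says.** Criterion 12, in the synopsis and again in Section 9.1.2, excludes "Warfarin taken within two weeks prior to the first dose of study drug". Table 3 gives the same two-week interval and permits novel oral anticoagulants, so a patient switched to one of these three weeks earlier is eligible. Section 9.6.3 adds: "Any contraindicated medications will be stopped or replaced by different medication and the subject will be required to observe the protocol-specified wash-out period".

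Section 6.1.1 gives the mechanism: "Warfarin blocks the generation of vitamin K hydroquinone by acting as an inhibitor of the vitamin K recycling". The hydroquinone is the cofactor for carboxylation. The abbreviation list expands PIVKA-II as "Protein Induced in Vitamin K Absence/Antagonist-II".

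Section 11.8 defines the secondary biomarker endpoints as "Plasma levels of the following biomarkers on Day 15 (end-of-treatment) and Day 22 compared to baseline", for uncarboxylated MGP, uncarboxylated osteocalcin, Activated Protein C and PIVKA-II. There is one pre-dose biomarker sample, on Day 1 (Section 9.6.8.2). The study is uncontrolled (Section 9.2.1) and no subgroup analyses are planned (Section 11.9). Medications taken "during the 30 days prior to the first dose of study drug will be recorded at screening/baseline" (Table 1, note 11).

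**The concern.** Three of the four secondary biomarkers measure failed carboxylation, which is what warfarin causes. A subject still recovering from warfarin on Day 1 would show these three falling by Day 15 and Day 22 without any study drug. Section 6.3.3 cites a randomized study in which vitamin K2 lowered the same three markers, so recovery and the hoped-for drug effect have the same sign. Protein C is vitamin-K-dependent (Section 6.3.3), so it would be expected to start low and rise.

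A single arm with one pre-dose sample cannot separate the two sources of change, and Section 11.8 pools all subjects. Section 9.4.1 explains why warfarin and vitamin K should not be combined, but neither it nor any other section says why two weeks was chosen or whether the biomarkers have settled by then. What is at stake is the reading of a named secondary endpoint in 15 subjects, ahead of a Phase 2b trial that is to ask whether the drug normalizes calcium-chelating proteins (Section 6.3.1).

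**Working it through.** **Inputs from the documents.** N = 15 with no sample size calculation (Section 11.2); 14-day warfarin interval; biomarker samples on Days 1, 15 and 22, that is 2 and 3 weeks after baseline; 95% confidence intervals for change from baseline (Section 11.6.3, which Section 11.8 follows). The plan states no biomarker effect, SD or recovery time, so there is no figure to reproduce.

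**Assumed inputs.** Number of recent users k, size of their excess, and its halving time h. None of these is in the documents.

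**Step 1: how much excess is left.** If the excess decays exponentially from a last dose 14 days before Day 1, the share left on Day 1 is 0.5^(14/h), and the share lost between Day 1 and Day 15 is 0.5^(14/h) − 0.5^(28/h), with h in days.

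| h (days) | Left on Day 1 | Lost Day 1 to 15 |
|---|---|---|
| 1 | 0.006% | 0.006% |
| 2 | 0.8% | 0.8% |
| 3 | 3.9% | 3.8% |
| 5 | 14.4% | 12.3% |
| 7 | 25.0% | 18.8% |
| 14 | 50.0% | 25.0% |

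At a halving time of two days or less the problem disappears.

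**Step 2: effect on the mean, starting from the on-warfarin level.** With an on-warfarin excess E, as a multiple of the other subjects' mean, the spurious shift in mean change is (k/15) × E × (share lost). For one user with E = 5 it is 0.3% of the other subjects' mean at h = 2 days, 1.3% at 3 days, 6.2% at 7 days and 8.3% at 14 days.

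**Step 3: effect on the mean, starting from the Day 1 level.** If recent users are at m times the others on Day 1, and h is now in weeks, the spurious fall at Day 15 as a share of mean baseline is

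(k/15)(m − 1)(1 − 2^(−2/h)) / [1 + (k/15)(m − 1)].

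- k = 2, m = 2, h = 2: 0.1333 × 0.50 / 1.1333 = 5.9%.
- k = 2, m = 2, h = 1: 0.1333 × 0.75 / 1.1333 = 8.8%.
- The same cases at Day 22 (replace 2/h by 3/h): 0.1333 × 0.646 / 1.1333 = 7.6% and 0.1333 × 0.875 / 1.1333 = 10.3%.
- Corners of k = 1 to 3, m = 1.5 to 4, h = 1 to 2 weeks at Day 15: 1.6% (k = 1, m = 1.5, h = 2) and 28% (k = 3, m = 4, h = 1).

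This version presupposes that some excess remains on Day 1, so 1.6% is not a floor. The 28% corner implies an on-warfarin level of 1 + 3/0.25 = 13 times the others.

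**Step 4: chance that anyone is affected.** The probability of at least one recent user among 15 is 1 − (1 − p)^15: 26%, 54% and 79% if 2%, 5% or 10% of the source population are recent users.

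**Step 5: cost of a summary without them.** The 95% CI half-width for a mean change is t(0.975, n − 1)/√n in SD units: 0.554 at n = 15, 0.577 at 14, 0.604 at 13 and 0.635 at 12. These intervals are 4%, 9% and 15% wider, if the SD is unchanged.

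**Step 6: entry routes.** Section 9.6.3 foresees stopping a contraindicated drug and observing its washout. The synopsis, however, sets a "Screening visit (within seven days prior to the first dose of study drug", and Section 13.2 requires consent "before any study-related procedures, assessments, treatments, or protocol-required changes in the subject's ongoing management can be made". A 14-day washout begun after consent does not fit into a screening window of at most 7 days.

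**The case against.** The strongest objection is that the premise is not in the documents. Section 6.1.1 gives a mechanism, not a duration, and no recovery time is stated for any of the four markers. That stands, and it is why the point can only be conditional. A reader might infer from criterion 12 that the biomarker results are biased in the drug's favour. The documents do not support that, because they contain neither the recovery kinetics nor the share of recent users.

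A reader might also infer from Section 9.6.3 that patients will routinely be taken off warfarin in order to enter. Step 6 argues against this. Those affected would mostly have stopped or switched earlier for other reasons, and must still be judged clinically stable under inclusion criterion 3. That narrows the route without closing it.

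Nor does the arithmetic mean stand alone: medians and ranges are planned, and Section 11.8 allows transformations for skew and outliers. The median would be less affected by one or two subjects. The transformations are optional and depend on the data, and the planned interval is for the change itself.

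Much of the information is already collected: per-subject listings, the 30-day medication record, and INR at screening and Day 1 (though no INR limit is set). A careful reader could find a recent user. But the plan has no rule for using this information, and setting subjects aside after seeing the results would invite challenge.

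Finally, all analyses are descriptive and no decision rule rests on the biomarkers. This limits the consequence. It does not stop the changes being read as drug effects.

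**Conclusion.** The plan leaves a possible bias that it could not detect as written. Its size runs from nil (fast recovery, or no recent users) to material. With two users at twice the others' baseline and an excess halving every one to two weeks, it is about 6% to 9% of mean baseline at Day 15. All of those inputs are assumptions. For uncarboxylated MGP, uncarboxylated osteocalcin and PIVKA-II the bias would be a spurious fall; for Activated Protein C, a spurious rise would be expected. The primary endpoint, adverse event frequency, is not a biomarker change and is outside this point.

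This does not show that two weeks is the wrong interval, and it does not justify removing recent users from the main biomarker summary. It supports a low-cost supplementary analysis, specified before the data are seen.

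**What to change.** Leave eligibility, washout and the safety population unchanged. In Section 11.8, keep the all-subject summary and add:

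- a supplementary summary of each secondary biomarker's change at Day 15 and Day 22, excluding any subject whose 30-day pre-dose medication record shows warfarin;
- a display of the excluded subjects' individual Day 1, Day 15 and Day 22 values, with the date of their last warfarin dose.

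The cost is one extra table per biomarker, plus making sure that the last warfarin date is captured. If nobody is flagged, the supplementary summary equals the main one. If one to three subjects are flagged, its 95% CI is 4% to 15% wider at the same SD.

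One limit should be stated in the plan: stops more than 30 days before Day 1 are not captured. At a two-week halving time, 0.5^(31/14), or about 22% of the excess, would remain 31 days after the last dose.

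Separately, the stop-and-washout provision in Section 9.6.3, the seven-day screening window and the consent-first rule in Section 13.2 must be reconciled.
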